5.7.7 Management of hyperlipidemia and hyperglycemia

Treatment of hyperlipidemia should take into account the pre-treatment status and dietary habits. Blood tests to monitor hyperlipidemia must be taken in the fasting state. Grade 2 hypercholesterolemia (> 300 mg/dL or 7.75 mmol/L) or Grade 2 hypertriglyceridemia (>2.5 x ULN) should be treated with a 3-hydroxy-3-methyl-glutaryl (HMG)-CoA reductase inhibitor (e.g., atorvastatin, pravastatin) or appropriate lipid-lowering medication, in addition to diet. Patients should be monitored clinically and through serum biochemistry for the development of rhabdomyolysis and other adverse events as required in the product label/data sheets for HMG-CoA reductase inhibitors.

Note: Concomitant therapy with fibrates and an HMG-CoA reductase inhibitor is associated with an increased risk of a rare but serious skeletal muscle toxicity manifested by rhabdomyolysis, markedly elevated creatine kinase (CPK) levels and myoglobinuria, acute renal failure and sometimes death. The risk versus benefit of using this therapy should be determined for individual patients based on their risk of cardiovascular complications of hyperlipidemia.

Grade 3 **hyperglycemia** has been observed in patients receiving RAD001 therapy. In many cases in study RAD001 C2222, the affected patients had an abnormal fasting glucose at baseline.

Based on this finding, it is suggested that optimal glucose control should be achieved before starting a patient on RAD001 and should be monitored during RAD001 therapy.

5.7.8 Management of non-infectious pneumonitis

Both asymptomatic radiological changes (grade 1) and symptomatic non-infectious pneumonitis (grade 2 = not interfering with activities of daily living or grade 3 = interfering with activities of daily living and oxygen indicated) have been noted in patients receiving RAD001 therapy. Non-infectious pneumonitis has been associated with RAD001 and other mTOR inhibitors (Atkins 2004). In order to monitor for asymptomatic (grade 1) pulmonary infiltrates, a chest X-ray is required if a CT scan of chest is not used for bi-monthly disease evaluations. Additional chest CT scans may be performed, when clinically necessary. If non-infectious pneumonitis develops, a consultation with a pulmonologist should be considered. If the patient develops grade 3 pneumonitis, treatment with RAD001 should be interrupted and the patient should be treated as medically indicated (short course corticosteroids, oxygen, etc).

Management of non-infectious pneumonitis suspected to be associated with RAD001 and dose modifications instructions are provided in Table 3-2

Table 7 Management of non-infectious pneumonitis

Worst Grade Pneumonitis	Required Investigations	Management of Pneumonitis	RAD001 Dose Adjustment
Grade 1	CT scans with lung windows and pulmonary function testing including: spirometry, DLCO, and room air O₂ saturation at rest. Repeat chest x-ray/CT scan every 2 Cycles until return to baseline.	No specific therapy is required	Administer 100% of RAD001 dose.
Grade 2	CT scan with lung windows and pulmonary function testing including: spirometry, DLCO, and room air O₂ saturation at rest. Repeat each subsequent Cycle until return to baseline. Consider bronchoscopy *	Symptomatic only. Prescribe corticosteroids if cough is troublesome.	Reduce RAD001 dose until recovery to ≤ Grade 1. RAD001 may also be interrupted if symptoms are troublesome. Patients will be withdrawn from the study if they fail to recover to ≤ Grade 1 within 3 weeks.
Grade 3	CT scan with lung windows and pulmonary function testing including: spirometry, DLCO, and room air O₂ saturation at rest.; Repeat each subsequent Cycle until return to baseline. Bronchoscopy is recommended *	Prescribe corticosteroids if infective origin is ruled out. Taper as medically indicated.	Hold treatment until recovery to ≤ Grade 1. May restart protocol treatment within 2 weeks at a reduced dose (by one level) if evidence of clinical benefit. Patients will be withdrawn from the study if they fail to recover to ≤ Grade 1 within 2 weeks.
Grade 4	CT scan with lung windows and required pulmonary function testing includes: spirometry, DLCO, and room air O₂ saturation at rest. Repeat each subsequent Cycle until return to baseline. Bronchoscopy is recommended *.	Prescribe corticosteroids if infective origin is ruled out. Taper as medically indicated.	Discontinue treatment.

*A bronchoscopy with biopsy and/or bronchoalveolar lavage is recommended.

All interruptions or changes to study drug administration must be recorded.

5.8 Treatment compliance

Research center personnel will review the dosing instructions with subjects. Subjects will be asked to maintain a diary to record the drug administration (Appendix Y). Subjects will be asked to bring any unused drug and empty drug containers to the research center at their next visit. Research personnel will count and record the number of used and unused drug at each visit and reconcile with the patient diary.

Any unused Revlimid® (lenalidomide) should be returned to the patient for disposition in accordance with the RevAssist® program.

Any unused everolimus pills should be returned to the IDS pharmacy for appropriate handling and destruction.

5.9 Concomitant therapy-Lenalidomide

5.9.1 Recommended concomitant therapy

Subjects should receive full supportive care, including transfusions of blood and blood products, antibiotics, and antiemetics when appropriate

5.9.2 Anticoagulation Consideration

Lenalidomide increases the risk of thrombotic events in patients who are at high risk or with a history a thrombosis, in particular when combined with other drugs known to cause thrombosis. When lenalidomide is combined with other agents such as steroids (e.g. dexamethasone, prednisone), anthracyclines (Doxil, Adriamycin) and erythropoietin the risk of thrombosis is increased.

Subjects deemed by the principal investigator at heightened risk of venous thrombosis will receive prophylactic anticoagulation with the use of aspirin (81 or 325 mg) or some other form of prophylaxis as deemed appropriate. Low molecular weight heparin may be utilized in patients that are intolerant to ASA. Coumadin should be used with caution and close monitoring of INR.

Prophylactic anti-coagulation should be held for platelet counts \leq 50,000, and then restarted when platelet counts are \geq 75, 000.

5.9.3 Prohibited concomitant therapy

Concomitant use of other anti-cancer therapies outside of the study drugs, including radiation or other investigational agents is not permitted while subjects are receiving protocol therapy during the treatment phase of the study.

5.10 Concomitant Therapy – Everolimus (RAD001)

Patients will be instructed not to take any additional medications (including over-the-counter products) during the course of the study without prior consultation with the investigator. At each visit, the investigator will ask the patient about any new medications he/she is or has taken after the start of the study drug.

All Concomitant medications/Significant non-drug therapies taken \leq 30 days prior to start and after start of study drug, including physical therapy and blood transfusions, should be recorded.

The following restrictions apply during the entire duration of the study:

- No other investigational therapy should be given to patients.
- No anticancer agents other than the study medication should be given to patients. If such agents are required for a patient then the patient must first be withdrawn from the study.

-
- Co-administration with strong inhibitors of CYP3A4 (e.g., ketoconazole, itraconazole, ritonavir) or P-glycoprotein (PgP) should be avoided
 - Seville orange, star fruit, grapefruit and their juices affect P450 and PgP activity. Concomitant use should be avoided
 - Co-administration with moderate CYP3A4 inhibitors (e.g., erythromycin, fluconazole) or PgP inhibitors should be used with caution. If patient requires co-administration of moderate CYP3A4 inhibitors or PgP inhibitors, reduce the dose of RAD001 to 5 mg daily. Additional dose reductions to 5 mg every other day may be required to manage toxicities. If the inhibitor is discontinued the RAD001 dose should be returned to the dose used prior to initiation of the moderate CYP3A4/PgP inhibitor.
 - Avoid the use of strong CYP3A4 inducers. If patient requires co-administration of strong CYP3A4 inducers (i.e., phenytoin, carbamazepine, rifampin, rifabutin, Phenobarbital, St. John's wort), **the patient should be monitored as per protocol and discontinued from study treatment if progression occurs.** An increase in the dose of RAD001 from 10 mg up to 20 mg daily should be considered, using 5 mg increments. Enzyme induction usually occurs within 7-10 days, therefore RAD001 dose should be increased to 15 mg daily, 7 days after the start of the inducer therapy. If no safety concerns are seen within the next 7 days, the dose can be increased again to 20 mg daily. This dose of RAD001 is intended to achieve similar AUC to the range observed without inducers. However, there are no clinical data with this dose adjustment in patients receiving strong CYP3A4 inducers. If the strong inducer is discontinued the RAD001 dose should be returned to the dose used prior to initiation of the strong CYP3A4/PgP inducer.
 - No chronic treatment with systemic steroids or another immunosuppressive agents. Topical or inhaled corticosteroids are allowed.
 - RAD001 may affect the response to vaccinations making the response to the vaccination less effective. Live vaccines should be avoided while a patient is treated with RAD001.

Oral anticoagulants such as warfarin are CYP2C9 substrates and, as such, no interaction with RAD001 is expected. However, drug-drug interaction studies between macrolide antibiotics and warfarin have produced mixed outcomes and the disparity in these findings has led to the conclusion that multiple factors may alter the clearance of warfarin. The coadministration of RAD001 and oral anticoagulants is possible but should be subject to verification of coagulation (INR) once steady state is reached (after one week's treatment).

Examples are provided in Table 8. A comprehensive list of cytochrome P450 isoenzymes and CYP3A4 inhibitors, inducers, and substrates can be found at <http://medicine.iupui.edu/flockhart>. This website is continually revised and should be checked frequently for updates.

Table 8 Examples of clinically relevant drug interaction: substrates, inducers and inhibitors of isoenzyme CYP3A.

Substrates (competitive inhibition)	
Antibiotics ¹ : clarithromycin* erythromycin telithromycin* Anti-arrhythmics: quinidine Benzodiazepines: alprazolam diazepam midazolam triazolam Immune Modulators: cyclosporine tacrolimus (FK506) HIV Protease Inhibitors: indinavir* ritonavir* saquinavir* Prokinetic: cisapride Antihistamines: astemizole chlorpheniramine_	Calcium Channel Blockers: amlodipine diltiazem felodipine nifedipine nisoldipine nitrendipine verapamil HMG CoA Reductase Inhibitors ² : atorvastatin cerivastatin lovastatin simvastatin Miscellaneous: aprepitant buspirone haloperidol methadone pimozide quinine sildenafil tamoxifen trazodone vincristine
Inducers	
Carbamazepine Phenobarbital Phenytoin* Rifabutin*	Rifampin* St John's wort Troglitazone
Inhibitors	
Amiodarone Cimetidine Clarithromycin Delaviridine Diltiazem Erythromycin Fluvoxamine* Grapefruit juice Sevilla orange	Indinavir Itraconazole* Ketoconazole* Voriconazole* Posaconazole* Mibefradil Nefazodone* Nelfinavir* Troleandomycin Verapamil

Based on: Ingelman-Sundberg M, Human drug metabolising cytochrome P450 enzymes: properties and polymorphisms, Naunyn Schmiedebergs Arch Pharmacol. 2004 Jan;369(1):89-104. and [http://www.medicine.iupui.edu/flockhart/clinlist.htm as of July 13, 2006]

* asterisk denotes strong inhibition/ induction

Please note:

- strong inhibitor implies that it can cause ≥ 5 -fold increase in AUC or $\geq 80\%$ decrease in clearance of sensitive CYP substrates
- moderate inhibitor implies that it can cause 2 to 5-fold increase in AUC values or 50-80% decrease in clearance of sensitive CYP substrates.

(Distinction is not always categorical as interaction can vary according to conditions).

1. Macrolide antibiotics: Azithromycin is not a CYP3A substrate. It may therefore be employed where

antibiotherapy with a macrolide is desirable in a patient being treated with RAD001

2. Statins: Atorvastatin and pravastatin may be associated with RAD001, since a PK interaction study has shown that there is no relevant PK interaction.

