5.7.6 Management of stomatitis/oral mucositis/mouth ulcers

Stomatitis/oral mucositis/mouth ulcers due to RAD001 should be treated using local supportive care. Please note that investigators in earlier trials have described the oral toxicities associated with RAD001 as mouth ulcers, rather than mucositis or stomatitis. If your examination reveals mouth ulcers rather than a more general inflammation of the mouth, please classify the adverse event as such. Please follow the paradigm below for treatment of stomatitis/oral mucositis/mouth ulcers:

1. For mild toxicity (Grade 1), use conservative measures such as **non-alcoholic mouth wash or salt water (0.9%) mouth wash** several times a day until resolution.
2. For more severe toxicity (Grade 2 in which case patients have pain but are able to maintain adequate oral alimentation, or Grade 3 in which case patients cannot maintain adequate oral alimentation), the suggested treatments are **topical analgesic mouth treatments (i.e., local anesthetics such as benzocaine, butyl aminobenzoate, tetracaine hydrochloride, menthol, or phenol)** with or without **topical corticosteroids**, such as triamcinolone oral paste 0.1% (Kenalog in Orabase[®]).
3. Agents containing hydrogen peroxide, iodine, and thyme derivatives may tend to worsen mouth ulcers. It is preferable to avoid these agents.
4. Antifungal agents must be avoided unless a fungal infection is diagnosed. In particular, systemic imidazole antifungal agents (ketoconazole, fluconazole, itraconazole, etc.) should be avoided in all patients due to their strong inhibition of RAD001 metabolism, thereby leading to higher RAD001 exposures. Therefore, topical antifungal agents are preferred if an infection is diagnosed. Similarly, antiviral agents such as acyclovir should be avoided unless a viral infection is diagnosed.

Note: Stomatitis/oral mucositis should be appropriately graded using the functional grading given on the NCI-CTC for adverse events, version 3.0.

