13.5 Appendix E – List of CYP450 and PgP Interacting Drugs

Agents that may Increase Everolimus Blood Concentrations

CYP3A4 Inhibitors and PgP Inhibitors: In healthy subjects, compared to everolimus treatment alone there were significant increases in everolimus exposure when coadministered with: ketoconazole (a strong CYP3A4 inhibitor and a PgP inhibitor) - C_{max} and AUC increased by 3.9- and 15.0-fold, respectively; erythromycin (a moderate CYP3A4 inhibitor and a PgP inhibitor) - C_{max} and AUC increased by 2.0- and 4.4-fold, respectively; verapamil (a moderate CYP3A4 inhibitor and a PgP inhibitor) - C_{max} and AUC increased by 2.3- and 3.5-fold, respectively. Concomitant strong or moderate inhibitors of CYP3A4 and PgP inhibitors should not be used. Due to significant increases in exposure of everolimus, co-administration with strong or moderate inhibitors of CYP3A4 (e.g., ketoconazole, itraconazole, clarithromycin, atazanavir, nefazodone, saquinavir, telithromycin, ritonavir, amprenavir, indinavir, nelfinavir, delavirdine, fosamprenavir, voriconazole, aprepitant, erythromycin, fluconazole, grapefruit juice, verapamil or diltazem) or P-glycoprotein (PgP) should be avoided.

Agents that may Decrease Everolimus Blood Concentrations

CYP3A4 Inducers: In healthy subjects, co-administration of everolimus with rifampin, a strong inducer of CYP3A4, decreased everolimus AUC and C_{max} by 64% and 58% respectively, compared to everolimus treatment alone. An increase in the everolimus dose is recommended when co-administered with a strong CYP3A4 inducer (e.g., dexamethasone, phenytoin, carbamazepine, rifampin, rifabutin, phenobarbital).

Agents whose Plasma Concentrations may be Altered by Everolimus

Studies in healthy subjects indicate that there are no clinically significant pharmacokinetic interactions between everolimus and the HMG-CoA reductase inhibitors atorvastatin (a CYP3A4 substrate) and pravastatin (a non-CYP3A4 substrate) and population pharmacokinetic analyses also detected no influence of simvastatin (a CYP3A4 substrate) on the clearance of everolimus

Drug Interactions with Lenalidomide

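### Section 5.10 allows moderate CYP3A4 and PgP inhibitors that Appendix E rules out, and its fixed 5 mg everolimus target gives no upfront cut to a patient already on 5 mg daily or less

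*Combined protocol and SAP*

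**What the plan says.** Three current parts of the protocol deal with everolimus and metabolic inhibitors.

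- **Section 5.10** introduces its list of concomitant-therapy rules with "The following restrictions apply during the entire duration of the study". It says to avoid strong inhibitors. For the next class down it says: "Co-administration with moderate CYP3A4 inhibitors (e.g., erythromycin, fluconazole) or PgP inhibitors should be used with caution". The dose rule is "If patient requires co-administration of moderate CYP3A4 inhibitors or PgP inhibitors, reduce the dose of RAD001 to 5 mg daily", followed by "Additional dose reductions to 5 mg every other day may be required to manage toxicities". When the inhibitor stops, everolimus goes back to its previous dose.
- **Appendix E** states: "Concomitant strong or moderate inhibitors of CYP3A4 and PgP inhibitors should not be used". The list that follows includes erythromycin, fluconazole, verapamil and diltiazem.
- **Section 5.7.6**, on mouth ulcers, says "systemic imidazole antifungal agents (ketoconazole, fluconazole, itraconazole, etc.) should be avoided in all patients due to their strong inhibition of RAD001 metabolism" and prefers topical antifungals.

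The exclusion criterion in Section 5.4.2 makes patients who are receiving CYP450 inhibitors or inducers ineligible and refers to Appendix E. Section 5.10 itself sends the reader to Table 8 and a website, not to Appendix E.

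On dose, Table 1 (Section 5.1) assigns everolimus 5 mg daily at levels -1 and 1 to 4, 10 mg daily at level 5 only, and 5 mg every other day at level -2. Table 4 (Section 5.7.1) gives the reduction ladder: 10 mg daily, 5 mg daily, 5 mg every other day.

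**The concern.** An investigator whose patient needs an antibiotic or antifungal during treatment finds two instructions that cannot both be followed. Section 5.10 allows erythromycin or fluconazole with care; Appendix E says not to combine them with everolimus. Fluconazole is even classed differently: a moderate inhibitor in Section 5.10, a strong one in Section 5.7.6. The situation is foreseeable. The everolimus safety summary in Section 3.5 lists infections and stomatitis among the most common reactions, and Section 5.9.1 provides for antibiotics as supportive care.

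The dose rule adds a second difficulty. It names a fixed target, not a step down from the current dose, and the target equals the assigned dose at five of the seven levels in Table 1. For those patients nothing changes when the inhibitor starts, and the every-other-day dose is offered only once toxicity has appeared. No PK samples are taken (Section 5.1.2, Appendix D), so raised exposure would not be measured. What is at stake is avoidable overexposure in individual patients.

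**Working it through.** The plan states no figure on this point, so there is none to reproduce. The check is a comparison of the rules followed by simple arithmetic.

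**Rules side by side**

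| Drug started on study | Section 5.10 | Appendix E | Section 5.7.6 |
|---|---|---|---|
| Erythromycin | Allowed with caution | Not to be used | Not addressed |
| Fluconazole (systemic) | Allowed with caution | Not to be used | Avoid in all patients |
| PgP inhibitors | Allowed with caution in this bullet | Not to be used | Not addressed |

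All three sections are current text. Section 5.4.2 decides who may enter, and does not say what may be started afterwards.

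**Inputs for the dose rule**

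- Appendix E, Cmax and AUC in healthy subjects. Erythromycin: "AUC increased by 2.0- and 4.4-fold, respectively". Verapamil: "AUC increased by 2.3- and 3.5-fold, respectively". The AUC factors f are therefore 4.4 and 3.5.
- Table 8 notes: a moderate inhibitor raises AUC 2- to 5-fold in general.
- Section 5.3.2: for daily dosing, AUC is dose-proportional between 5 and 10 mg. Using proportionality outside that range is an assumption.
- 5 mg every other day is taken as a mean of 2.5 mg/day.

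**Formulas**

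- Equivalent daily dose = dose after adjustment × f.
- Relative exposure = equivalent daily dose ÷ the dose in force when the inhibitor starts.

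| Case | Verapamil (3.5) | Erythromycin (4.4) | General range (2 to 5) |
|---|---|---|---|
| 5 mg daily, unchanged under Section 5.10 | 5 × 3.5 = 17.5 mg/day; 17.5/5 = 3.5 | 5 × 4.4 = 22 mg/day; 22/5 = 4.4 | 10 to 25 mg/day; 2 to 5 |
| 10 mg daily cut to 5 mg under Section 5.10 | 17.5 mg/day; 17.5/10 = 1.75 | 22 mg/day; 22/10 = 2.2 | 10 to 25 mg/day; 1.0 to 2.5 |
| 5 mg every other day, 5 mg daily target applied literally | 17.5 mg/day; 17.5/2.5 = 7.0 | 22 mg/day; 22/2.5 = 8.8 | 10 to 25 mg/day; 4 to 10 |
| 5 mg daily stepped down to every other day | 2.5 × 3.5 = 8.75 mg/day; 8.75/5 = 1.75 | 2.5 × 4.4 = 11 mg/day; 11/5 = 2.2 | 5 to 12.5 mg/day; 1.0 to 2.5 |

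The first two rows have the same absolute exposure and differ only relative to the dose in force. The last row halves the first (8.75/17.5 = 11/22 = 0.5) and matches the relative excess that Section 5.10 already accepts for a 10 mg patient.

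**Who could be affected**

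Section 10.6 says 21 of the 30 escalation places were needed, so escalation appears complete. Newly enrolled patients would be the 15 + 9 = 24 in the expansion cohorts. That is not a strict upper bound, since escalation patients may still be on treatment. How many would take an inhibitor is not given.

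**The case against.** The strongest reply is that the texts can be read together: avoid these drugs, and if one is required, use care and cap everolimus at 5 mg. Appendix E itself moves from a ban to advice to avoid, and the dose step in Section 5.10 applies only where the drug is required. The replacement proposed here also has two layers. This softens the conflict but does not remove it. Section 5.10 never says to avoid this class, it offers fluconazole as an example of acceptable use, and it does not point to Appendix E.

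Safeguards also exist. The entry exclusion removes patients already on inhibitors, Section 5.10 requires consultation before any new medication, and Table 6 and Section 5.7.4 govern toxicity. These narrow the problem to drugs newly started on study, but the toxicity rules act only after harm appears.

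On the dose rule, a fixed ceiling is a defensible idea, and no passage shows that relative rather than absolute exposure drives toxicity. That stands, and it is why this half is secondary.

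A reader might infer three stronger things that the documents do not support:

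- That a 5 mg patient ends up with more drug than a 10 mg patient. The absolute exposures are equal.
- That the dose gap will certainly affect the expansion cohorts. Table 1 leaves the MTD open. If it is level 5, the gap reaches only patients already reduced to 5 mg daily or less.
- That the MTD finding was distorted by inhibitor use in cycle 1. Nothing in the documents reports such use.

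**Conclusion.** The contradiction is an error in the current text and should be corrected whatever the MTD turns out to be. It leaves sites with opposite instructions for drugs that patients on this regimen may well need.

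The dose-step defect is real but conditional. If the MTD is a 5 mg daily level, the upfront step reduces nobody treated at that dose; if it is level 5, only patients already reduced are missed. For a 5 mg patient the size is about 3.5 to 4.4 times the assigned exposure with the two moderate inhibitors quantified in Appendix E, or 2 to 5 times over the general range in Table 8. These figures assume that healthy-subject factors carry over to patients and that AUC stays proportional to dose beyond the documented 5 to 10 mg daily. The number of patients affected cannot be estimated from the documents. This is a patient-safety wording error that should be fixed; it does not undermine the trial's design or its analysis.

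**What to change.** Amend the bullet on moderate inhibitors in Section 5.10:

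1. State that strong or moderate CYP3A4 inhibitors and PgP inhibitors are to be avoided on study, with a cross-reference to Appendix E.
2. Remove fluconazole as an example of permitted use, and point to the alternatives the protocol already names: azithromycin where a macrolide is wanted (Table 8 notes) and topical antifungals for oral infection (Section 5.7.6).
3. If a moderate CYP3A4 or PgP inhibitor is truly required, reduce everolimus by one Table 4 level when it starts: 10 mg to 5 mg daily, or 5 mg daily to 5 mg every other day. Never increase the dose. Keep the existing return to the prior dose when the inhibitor stops.

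Table 4 has no level below 5 mg every other day, so patients on that dose rely on avoidance and on the rule against any increase. A 10 mg patient who must take an inhibitor would still reach 17.5 to 22 mg/day equivalent, as now; the gain there comes from avoidance.

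The cost is amendment wording for one bullet, with no new visits, samples, data or patients. The differing everolimus starting doses (10 mg in the Section 5.1 narrative and Table 4; 5 mg in the Synopsis, Table 1 and Section 5.6.2) are a separate item. Table 1 is followed here.
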